DPR has also been studied in the treatment of severely injured trauma patients and has shown a decrease in days until closure with improved outcomes [10, 11]. A randomized controlled study of 103 subjects requiring damage control surgery, i.e. open abdominal cavities, found that peritoneal resuscitation reduced the time to definitive abdominal closure, reduced intra-abdominal infections and reduced mortality [11].

Title: Direct Peritoneal Resuscitation in Gastroschisis

PI: [name]

Sponsor: UAMS

Exposure of the abdominal viscera and its placement in a silo puts the neonate in a metabolically stressed state. Using DPR has been shown to counteract the systemic inflammatory response, leading to dilation of arterioles in the intestine resulting in reduced organ ischemia and cellular hypoxia [12].

Several case series have demonstrated safety of peritoneal dialysis in infants with recent abdominal surgery and intestinal perforation [13-15]. In pediatric patients, peritoneal resuscitation has been used in two infants with perforated NEC who were too unstable to undergo laparotomy. Both survived and went on to undergo laparotomy [16].

We consider the patient with gastroschisis as an equivalent to the general surgery patient with the open abdomen and that adjunctive DPR treatment may be able to accelerate abdominal closure and improve outcomes.

Ultrasounds

Optimal timing to begin feeds in neonates with gastroschisis remains unclear. A previous study performed by our research group concluded that bedside ultrasound is a feasible tool to detect return of bowel function in neonates with gastroschisis [17].

Study Summary

This is a prospective double-arm study designed to evaluate the tolerability of direct peritoneal resuscitation (DPR) in neonates with gastroschisis. The experimental arm (DPR group) will receive adjuvant DPR with standard treatment for gastroschisis (staged silo closure). The control arm (SoC group) will receive standard treatment for gastroschisis without DPR. The objectives are (1) to determine if subjects treated with DPR will have a more benign hospital stay as measured by time to full enteral feeds of 100 kcal/kg/day and (2) to monitor the effect of Dianeal 1.5% dialysis solution on the hemodynamics, serum electrolytes, lactic acid, respiratory function, and other parameters.

Hypothesis

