Hypotheses: We hypothesize that the DPR group will have a more benign hospital course as measured by time to full enteral feeds of 100 kcal/kg/day. We will also assess time to abdominal wall closure, time on TPN, length of hospital stay and intestinal motility post-closure using bedside ultrasounds. Secondly, we hypothesize that there will be no deleterious effects related to introducing the peritoneal dialysis solution into the silo.

Study Objectives

Primary Objectives:

1. To demonstrate that subjects treated with DPR will have a more benign hospital course as measured by time to full enteral feeds. The primary outcome measure will be time to full feeds of 100 kcal/kg/day. Secondary outcomes will include length of time until abdominal wall closure, time on TPN, time to intestinal motility, and total days in the hospital.
2. To demonstrate that the use of DPR in neonates with gastroschisis treated with staged silo closure will result in no significant changes in commonly measured clinical and laboratory safety parameters. This will be measured with more frequent clinical and laboratory assessments for the DPR group. Vital signs and strict intake and output will be monitored every 6 hours for 48 hours after the maximum dialysate infusion volume has been reached, then every 12 hours. Sodium, potassium, blood glucose and lactate levels will be monitored every 6 hours via heelstick, central/arterial line or venipuncture

Title: Direct Peritoneal Resuscitation in Gastroschisis

PI: [name]

Sponsor: UAMS

per NICU standard practice for 24 hours after the maximum dialysate infusion volume has been reached, then every 12 hours through Post-Closure Day 1.

Investigational Product

Dianeal PD-2 1.5% is a sterile, nonpyrogenic, hypertonic peritoneal dialysis solution containing dextrose, a monosaccharide, as the primary osmotic agent. Routine peritoneal dialysis in neonates and infants utilizes up to 40 mL/kg of dialysate per dwell. It will be administered via a 10 mm flat JP drain as a bolus infusion every 6 hours until the abdominal wall is closed (generally 3-5 days), but not to exceed 7 days maximum. The initial bolus infusion will be 10 mL/kg of Dianeal 1.5%. If tolerated, each subsequent infusion will be increased by 10 mL/kg of Dianeal 1.5% up to a goal infusion of 40 mL/kg (to a maximum volume of 100 mL) as tolerated.

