The DPR group will be placed in a silo within 2 hours of admission to the NICU with a drain placed at the top of the silo as described below. At the time of silo placement for staged procedure, the JP drain will be placed intra-abdominally beneath the fascia at the base of the small bowel mesentery. Subjects will be treated with adjuvant direct peritoneal resuscitation (DPR) until the abdomen is closed, which is usually four to five days. No additional incisions will be made.

Set-up of Silo

The silo will be placed within 2 hours of admission to the NICU as per standard of care. Through the top of the silo a flat 10 mm JP drain will be placed and secured with suture and sterile, adhesive tape at the top of the silo to create a seal. This drain will allow for aspiration of peritoneal fluid for specimen collection and instillation of Dianeal 1.5% (DPR group only).

Drain manipulation

The JP drain will be steriley placed through top of the silo at time of the silo placement into abdominal cavity. A closed system will be created using Medline One-link Needle-free IV connector to the drain to allow for sterile placement of the dialysate. There will not be any planned drain replacements. If the drain or silo replacement is necessary due to unforeseen circumstances, the abdomen will be prepped in standard sterile fashion and the silo with drain will be replaced in same manner as when it was initially placed. There will be no increased risk of underlying infection with placement of the silo or drain.

Set-up for DPR

The dialysate fluid will be placed in syringe under sterile conditions in the Research Pharmacy. The syringe will then be connected to the JP drain via a needle free IV connector. The connector will be cleaned with an alcohol wipe at the time of fluid instillation into the JP drain.

1. Instillation of fluid - Process will be repeated every 6 hours (\pm 30 minutes) until abdomen is closed.
 - a. Fluid will be warmed at bedside using dry heat not to exceed 37°C/98°F.
 - b. An initial bolus of 10 mL/kg of Dianeal 1.5% via the JP drain will be given. If tolerated, each subsequent bolus will be increased by 10 mL/kg of Dianeal 1.5% up to a goal infusion of 40 mL/kg of Dianeal 1.5% (to a maximum volume of 100 mL) as tolerated via the JP drain.
 - c. The maximum dose that will be administered, based on a historical data (CHND), is 100 mL.

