- Hospital Discharge
- Adverse events

Post-Discharge Follow-up (up to 90 days following hospital discharge)

- Chart review or phone call
- Adverse events

Risks and Benefits

Both groups will have the same underlying risks secondary to gastroschisis repair, anesthesia and surgery independent of the silo placement. These risks include allergic reaction to medicines, breathing problems (including problems requiring intubation and ventilation), bleeding, infection, inflammation of peritoneum, organ injury, problems with digestion and malabsorption, dysmotility, and abdominal wall hernia.

As this is a novel procedure, the risk for infection secondary to placement and retention of the JP drain, for the DPR group, is unknown. However, given that the JP drain will be steriley placed and secured to the silo bag under sterile conditions, we estimate that the risk of JP drain placement and retention in the silo would not be appreciably higher than the risk of infection secondary to standard gastroschisis repair (12.5%). Additionally we estimate that the risk for infection secondary to placement and retention of JP drain within the peritoneum beneath the fascia at the base of the small bowel mesentery would not be substantially higher than the risk of infection secondary to standard gastroschisis repair (12.5%).

Subjects may also have the risk of potential for loss of confidentiality. Measures to protect the confidentiality of study participants will be implemented as described in the Data Handling and Recordkeeping section below.

Additional risks for babies who undergo DPR treatment may include electrolyte imbalances, which will be monitored via laboratory values.

Title: Direct Peritoneal Resuscitation in Gastroschisis

PI: [name]

Sponsor: UAMS

Babies in the DPR group are at risk for Encapsulating Peritoneal Sclerosis, allergic reaction to corn (including anaphylaxis), and possible reactions with insulin or other concomitant medications and treatments.

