Demographic variables will be assessed for differences between groups. Categorical variables will be examined using Fisher's Exact Test or Chi Square Test. Continuous data will be examined using Students' T-test. All tests will be two-sided assuming a significance level of 5%. The dependent variable will be tested to ensure the assumption of normality is met.

The primary outcome measure is time to full enteral feeds of 100 kcal/kg/day. Using a two-sample t-test, we estimated that a sample size of 20 in each of the two groups will yield at least 80% power to detect a 6-day difference in mean time to goal enteral feeds (100 kcal/kg/day) assuming a common standard deviation of 7 and a two-sided significance level of 5%.

The proposed data analyses and sample size calculations were conducted with the support of statisticians at ACRI using SAS® Software, Version 9.4[24].

Ethical Considerations

This study is to be conducted according to applicable government regulations and Institutional research policies and procedures.

Title: Direct Peritoneal Resuscitation in Gastroschisis

PI: [name]

Sponsor: UAMS

The parent(s)/LAR of each potential subject identified as meeting inclusion criteria for this study will be approached to discuss participation in this study by trained study personnel. The person obtaining consent will go over the informed consent comprehensively with the parent(s)/LAR. The risks and rationale of this study will be outlined and all questions will be answered. The volunteer natures of this project will be emphasized, including uninhibited withdrawal from the study at any time. No coercion or undue influence will be used in the consent process. A copy of the signed consent will be given to the subject's parent(s)/LAR, and the informed consent process will be documented in each subject's research record in a separate process note.

Ways of consenting parent(s)/LAR:

1. Mother or father (if mother and father are married)/LAR consented prenatally in OB/GYN clinic.
2. Mother or father (if mother and father are married)/LAR consented after birth via faxed consent to the OB unit and returned to PI. The faxed consent will then be witnessed by bedside nurse.
 - a. The person obtaining consent will fax a consent form to the OB unit and conduct the consent process conversation by phone once the mother or father/LAR has the form in hand.

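### Primary objective 2 seeks to demonstrate safety through an absence of significant change, which 20 infants per arm cannot show: a half-SD shift would be missed about 66% of the time

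*Combined protocol and SAP*

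**What the plan says.** The Study Objectives section lists two primary objectives. The second is to demonstrate that DPR with staged silo closure "will result in no significant changes in commonly measured clinical and laboratory safety parameters". The measures it then names are vital signs, intake and output, sodium, potassium, glucose and lactate. The Hypothesis section is broader: "we hypothesize that there will be no deleterious effects related to introducing the peritoneal dialysis solution into the silo". The Study Summary words the same aim more modestly, as "to monitor the effect of Dianeal 1.5% dialysis solution on the hemodynamics, serum electrolytes, lactic acid, respiratory function, and other parameters".

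The Data Analysis section names Fisher's exact or chi-square tests for categorical variables and Student's t-test for continuous ones, and adds "All tests will be two-sided assuming a significance level of 5" per cent. Its only sizing statement concerns time to full enteral feeds: "a sample size of 20 in each of the two groups will yield at least 80% power to detect a 6-day difference". It gives no equivalence or non-inferiority margin, no confidence interval and no sizing for safety.

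On infection, Risks and Benefits calls the drain-related risk unknown, but estimates that it "would not be appreciably higher than the risk of infection secondary to standard gastroschisis repair (12.5" per cent). Drain manipulation says: "There will be no increased risk of underlying infection with placement of the silo or drain".

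**The concern.** Failing to find a difference is not evidence that there is none, and with 20 infants per arm it is weak evidence even against sizeable differences. The objective is one of two primary objectives, in neonates, for what the protocol itself calls a novel procedure. As worded, a p-value above 0.05 in a small sample could be reported as demonstrated safety. The reverse error is also open: if each safety parameter were tested at 5%, a harmless treatment could easily produce a nominally significant change somewhere. The protocol states no rule for telling these situations apart.

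**Working it through.** **Inputs.** From Data Analysis: 20 per arm, two-sided 5%; for feeds, a difference of 6 days and SD of 7. From Risks and Benefits: 12.5% infection with standard repair. The half-SD shift and the doubling of infection are scenarios chosen here; the protocol gives neither. All 20 infants per arm are assumed to be analysed.

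**1. The plan's own figure.** Standardised difference 6/7 = 0.857; noncentrality 0.857 × √(20/2) = 2.71; 38 degrees of freedom. Two-sided t-test power is 75.2% (77.4% by normal approximation), against the stated minimum of 80%; the t-test needs 23 per arm. This is a separate matter, and nothing below depends on it. There is no corresponding safety figure to reproduce.

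**2. Continuous safety measures (those objective 2 names).**
- True shift of 0.5 SD: noncentrality 0.5 × √10 = 1.58, power 33.8%, missed 66.2%.
- Shift detectable with 80% power: about 0.91 SD.
- 95% interval half-width: t(0.975, 38) × √(2/20) = 2.024 × 0.316 = 0.64 SD. An observed difference of zero is therefore still compatible with a true shift of up to 0.64 SD either way.

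**3. Infection (an illustration; objective 2 does not list it).** Enumerating all 21 × 21 outcomes for 12.5% v 25%, 20 per arm:

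| Test | Power | Missed |
|---|---|---|
| Fisher's exact | 9.8% | 90.2% |
| Chi-square, uncorrected | 17.0% | 83.0% |
| Chi-square, continuity-corrected | 8.3% | 91.7% |

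The average expected count is 20 × (0.125 + 0.25)/2 = 3.75 per arm, below 5, so Fisher is the natural choice. Its power reaches 80% only at a DPR rate of about 57%.

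**4. What reassuring results would exclude.**
- No events in 20: upper two-sided 95% limit 1 − 0.025^(1/20) = 16.8%.
- 3/20 in each arm: Newcombe 95% interval for the difference, about −23 to +23 percentage points.

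**5. The reverse error.** Four analytes plus four vital signs, each tested at 5% and assumed independent: 1 − 0.95^8 = 34% chance of at least one false positive. Correlation lowers this.

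**6. Could the trial be sized for a formal safety claim?** Non-inferiority at 12.5% in both arms, one-sided 2.5%, 80% power: n = (1.96 + 0.84)² × 2 × 0.125 × 0.875 / margin². For assumed margins of 10, 12.5 and 15 points this gives 172, 110 and 77 per arm. Estimation is the realistic course at 20 per arm.

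**The case against.** Four points deserve weight.

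- *The Study Summary says monitor, and calls this a tolerability study.* True, and that wording is supportable. But the formal primary objective says demonstrate, so the two need aligning.
- *Significant may mean clinically significant.* Possibly. The protocol has numerical discontinuation limits and adverse-event grades, but ties none of them to objective 2, so that reading gives no criterion either.
- *A stopping rule exists.* Study Discontinuation halts the trial once more than three DPR infants meet any one criterion. If every infection counted towards one criterion (an assumption), four or more of 20 would occur with probability 77% at a 25% rate and 23% at 12.5%. A reader might infer from the 90% figure that doubled infection would go unnoticed. The documents do not support that: the figure concerns a between-arm test only. Equally, the rule looks at DPR infants alone and cannot support a comparative safety conclusion.
- *No text assigns a 5% test to each safety parameter.* Correct. Data Analysis opens with demographics and does not link any test to objective 2. A reader might infer that the plan would declare DPR unsafe after one p < 0.05 among many. It says no such thing, so the 34% is conditional. If the listed tests do not apply to safety, objective 2 has no planned analysis at all.

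The infection figure must also stay an illustration. Infection falls under the broader hypothesis, is collected (Data to be obtained, item 4) and is an adverse event of special interest, but objective 2 does not list it.

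**Conclusion.** The concern holds as a defect of inference in the wording and analysis of objective 2. At 20 per arm, a non-significant comparison leaves shifts of around half an SD in the named laboratory and vital-sign measures quite possible (66% missed). For infection, the illustrative doubling is missed in 83% to 92% of trials, depending on the test. These figures assume complete data in 20 infants per arm; losses would make them worse.

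The two infection statements need reconciling, but a reader should not infer an outright contradiction. The Drain manipulation sentence directly follows text on unplanned replacement of the drain or silo and may refer only to that.

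This should be fixed before analysis. Enrolment, treatment and data collection are unaffected.

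**What to change.** Reword objective 2 as estimation, in line with the Study Summary, and add to Data Analysis:

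1. **Continuous measures.** Between-arm difference with 95% interval for mean sodium, potassium, glucose and lactate and for vital signs, using only time points sampled in both arms. For laboratory values these are the 24-hourly routine draws. DPR infants are also sampled every 6 and then every 12 hours, with extra glucose checks on the first day of treatment.
2. **Infection.** Between-arm difference in the proportion of infants with infection, with 95% interval.
3. **Threshold crossings, if compared.** Use one named set of the protocol's existing limits, at matched times only. The limits vary by section: potassium is below 3.0 in the exclusions and Safety Monitoring, below 2.5 for discontinuation, and 2.0–2.5 in the adverse-event table. Comparing infants who ever crossed a limit across all samples would count against DPR simply because it is sampled more often. Report events found only by the extra DPR sampling descriptively, for that arm.
4. **Interpretation.** State that p > 0.05 will not be reported as no change or as safe, that the conclusion is limited to the excess the upper confidence limit rules out, and that 0/20 excludes only rates above about 17%.
5. **Consistency.** Reconcile the infection statement in Drain manipulation with Risks and Benefits.

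The cost is wording only, with no extra infants, blood or procedures. The downside is a weaker safety claim.

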The investigational product will be kept in a secure, limited-access storage in the ACRI research pharmacy under the direction of the research pharmacists who will be responsible for maintaining the supply according to the manufacturer's specifications, dispensing the drug for administration, and maintaining all drug accountability logs.

Study Population

We will prospectively enroll all neonates with the diagnosis of gastroschisis presenting to ACH within 12 hours after birth for whom consent is signed by the parent(s)/LAR. We anticipate enrolling 40 subjects at Arkansas Children's Hospital. All subjects that have their abdominal wall defect closed will be defined as having completed active participation in the study.

Eligibility Criteria

Inclusion criteria:

- Diagnosis of Gastroschisis
- Male or Female, any ethnicity
- Neonates [18]

Exclusion criteria:

- Primary gastroschisis repair
- Vanishing gastroschisis
- Encapsulating peritoneal sclerosis
- Infants < 2 kg and < 34 weeks gestation
- Infants > 12 hours at enrollment
- Severe hypotension, defined as either:
 - Mean arterial blood pressure (MAP) < gestational age in weeks, or
 - Systolic blood pressure (BP) < 45 or diastolic BP < 20
- Severe Hypertension defined as Systolic BP > 90 or diastolic > 60
- Culture-positive sepsis
- Known or strongly suspected inborn errors of metabolism
- Significant cardiac disorders, including cyanotic congenital heart disease, ductal-dependent congenital heart disease, and critical congenital heart disease (lesions requiring surgery or catheter-based intervention in the first year of life)
- Respiratory failure, defined as any requirement of positive pressure ventilation at the time of enrollment, or FiO₂ > 50%

Title: Direct Peritoneal Resuscitation in Gastroschisis

PI: [name]

Sponsor: UAMS

- Any other condition, that, in the opinion of the investigator, might interfere with the safe conduct of the study or place the subject at increased risk
- Lactic acidosis with at least one or more of the following:
 - Characterized by increased blood lactate levels ($> 5 \text{ mmol/L}$) on two occasions at least 6 hours apart
 - Severe metabolic acidosis with an arterial pH ≤ 7.0
 - Bicarbonate < 14 or $\text{CO}_2 < 12$
 - Base excess of $> -10 \text{ mEq/L}$
- Neonatal Acute Renal Failure, defined as serum creatinine $> 2.0 \text{ mg/dL}$ with anuria in the first 12 hours of life
- Neonatal Acute Hepatic Failure, defined as INR ≥ 3 [19]

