- Liver function test abnormalities defined as AST > 200 , ALT > 200 , GGT > 100 [19]
- Electrolyte abnormalities, defined as:
 - Sodium < 130 or $> 150 \text{ mEq/L}$
 - Potassium < 3.0 or $> 6.5 \text{ mEq/L}$
- Hyperglycemia ($> 150 \text{ mg/dL}$) or hypoglycemia ($< 40 \text{ mg/dL}$)

Note: Potentially eligible subjects may be randomized and the silo placed according to the assigned study arm before all laboratory results are available. Laboratory values will be verified for eligibility prior to administration of DPR. Any ineligible subjects will be withdrawn from the study and may be replaced.

Randomization

The randomization schedule will be generated by the biostatistics department and the Principal Investigator (PI) will maintain a randomization log listing the subjects' ID and study arm assignment. Subjects will be randomized to either the DPR group or SoC group. If the subject is assigned to receive DPR, the ACRI Research Pharmacist will dispense the 1.5% Dianeal solution. The PI will calculate the dose to be distributed based on the subject's weight at the time of enrollment and administer the appropriate volume of 1.5% Dianeal solution as per instructions in the *Investigational Product* section.

Study Design and Procedures

This is a prospective double-arm study designed to evaluate the tolerability of direct peritoneal resuscitation (DPR) in neonates with gastroschisis. The experimental arm (DPR group) will receive adjuvant DPR with standard treatment for gastroschisis (staged silo closure). The control arm (SoC group) will receive standard treatment for gastroschisis only. All subjects will be placed in a silo shortly after birth and within 2 hours of admission to the NICU and subsequently serially reduced in silo with umbilical tape until the bowel contents are at the level of fascia and deemed suitable for closure.

A. SoC Group

[figure not shown]
The SoC group will be placed in silo within 2 hours of admission to the NICU per standard practice. These subjects will have no change in current clinical management by the neonatologists or pediatric surgeons and will not receive peritoneal dialysis fluid.

B. DPR Group

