¹¹ The clinical course of each AE should be followed until resolution, stabilization, or until it has been determined that the study treatment is not the cause.

Title: Direct Peritoneal Resuscitation in Gastroschisis

PI: [name]

Sponsor: UAMS

Schedule of Procedures and Assessments

Screening (Day of Birth from 0-12 hours)

- Informed Consent
- Randomization
- Silo placement (within 2 hours of admission to the NICU)
 - JP drain placed and secured per randomization
- Vital signs: heart rate (HR), respiratory rate (RR), MAP/BP, pulse oximetry (SpO₂)
- Weight
- Routine Daily labs per NICU standard practice:
 - Complete CBC
 - Magnesium
 - Renal Function Panel (sodium, potassium, chloride, CO₂, BUN, creatinine, calcium, phosphate, albumin, glucose)
- Research lab (both groups):
 - Lactate
- G-tube placement per NICU standard practice

Staged Reduction Day 1 (Day of Birth from 0-24 hours)

- Verify laboratory values for eligibility
- Instill DPR for DPR group every 6 hrs (± 30 minutes)
- Blood glucose within 1 hour prior to infusion and 1 hour (± 15 minutes) post-infusion for the first 24 hrs of DPR
- Vital signs every 6 hrs (± 30 minutes): HR, RR, MAP/BP, SpO₂
- Weight
- Strict intake/output every 6 hrs (± 30 minutes)
- DPR Group research labs every 6 hrs (± 30 minutes):
 - Sodium
 - Potassium
 - Glucose
 - Lactate
- Adverse events

Day of Life 1 - Day of Life 7

- Instill DPR for DPR group every 6 hrs (± 30 minutes) until abdomen is closed
- Blood glucose within 1 hour prior to infusion and 1 hour (± 15 minutes) post-infusion for the first 24 hrs of DPR
- Vital signs every 6 hrs (± 30 minutes) for 48 hours after maximum dialysate infusion volume (100 mL) is reached, then every 12 hrs (± 30 minutes): HR, RR, MAP/BP, SpO₂
- Weight
- Strict intake/output every 6 hrs (± 30 minutes) for 48 hours after maximum dialysate infusion volume (100 mL) is reached, then every 12 hrs (± 30 minutes)
- Routine daily labs per NICU standard practice:
 - Complete CBC
 - Magnesium
 - Renal Function Panel (sodium, potassium, chloride, CO₂, BUN, creatinine, calcium, phosphate, albumin, glucose)

Title: Direct Peritoneal Resuscitation in Gastroschisis

PI: [name]

Sponsor: UAMS

- SoC Group research lab (every 24 hrs (\pm 30 minutes) at the same time as routine daily labs:
 - Lactate
- DPR Group research labs every 6 hrs (\pm 30 minutes) for 24 hours after maximum dialysate infusion volume (100 mL) is reached, then every 12 hrs (\pm 30 minutes):
 - Sodium
 - Potassium

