7. Acute Kidney Injury (AKI): AKI will be staged using the “Neonatal AKI KDIGO Classification” Table below (Selewski *et al* [22]). Subjects who develop AKI > Stage 2 will be withdrawn from the study.

TABLE 1 Neonatal AKI KDIGO Classification

Stage	SCr	Urine Output
0	No change in SCr or rise <0.3 mg/dL	≥ 0.5 mL/kg/h
1	SCr rise ≥ 0.3 mg/dL within 48 h or SCr rise $\geq 1.5\text{--}1.9 \times$ reference SCr ^a within 7 d	<0.5 mL/kg/h for 6 to 12 h
2	SCr rise $\geq 2.0\text{--}2.9 \times$ reference SCr ^a	<0.5 mL/kg/h for ≥ 12 h
3	SCr rise $\geq 3 \times$ reference SCr ^a or SCr ≥ 2.5 mg/dL ^b or Receipt of dialysis	<0.3 mL/kg/h for ≥ 24 h or anuria for ≥ 12 h

Differences between the proposed neonatal AKI definition and KDIGO include the following:

^a Reference SCr will be defined as the lowest previous SCr value.

^b SCr value of 2.5 mg/dL represents <10 mL/min/1.73m².

Individual Subject Discontinuation

If a subject develops any of the individual subject discontinuation criteria below, the study drug will be immediately discontinued:

- Positive blood culture
- Documented peritonitis
- Lactic acid > 5 mmol/L
- pH < 7.1
- Sodium < 125 mEq/L or > 150 mEq/L
- Potassium < 2.5 mEq/L
- Continued hyperglycemia > 250 for more than 12 hours
- Definite (culture positive) sepsis
- Stage 3 AKI [22]

Title: Direct Peritoneal Resuscitation in Gastroschisis

PI: [name]

Sponsor: UAMS

Subjects who develop any of the individual subject discontinuation criteria will be evaluated and monitored until resolution of the adverse events and laboratory values have returned to baseline. These subjects will no longer receive DPR, but will continue with assessments per the schedule of procedures and assessments.

Study Discontinuation

The study will be stopped if more than 3 subjects in the DPR group develop any one of the individual subject discontinuation criterion above.

Adverse Events

For purposes of this study, the following will be considered adverse events of special interest if they occur before study completion:

1. Bradycardia: defined as a heart rate < 100 bpm for ≥ 20 seconds
2. Desaturation: defined as SpO₂ < 80% for ≥ 20 seconds
3. A sustained apnea event defined as lasting ≥ 20 seconds and coinciding with at least one of the following:
 - HR < 100 bpm
 - Desaturation (oxygen saturation < 80%)
4. Other AES of special interest have been adopted from England *et al.*'s adverse event tables for the Pediatric Trials Network (PTN) [23] (Appendix E).

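### An infant with one raised pre-dose lactate can start the lactate-containing dialysate while already above the limit that stops it; the pH and creatinine limits share the gap

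*Combined protocol and SAP*

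**What the plan says.** All references are to the combined protocol and SAP.

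- **Eligibility Criteria.** Any one of four items meets the lactic acidosis exclusion. The lactate item needs a value above 5 mmol/L "on two occasions at least 6 hours apart". The others are an arterial pH of 7.0 or lower, low bicarbonate or CO₂, and a base excess item.
- **Note at the end of Eligibility Criteria.** Randomization and silo placement may come before all results are back. Then: "Laboratory values will be verified for eligibility prior to administration of DPR". And: "Any ineligible subjects will be withdrawn from the study and may be replaced".
- **Schedule of Procedures and Assessments.** Screening (first 12 hours of life) lists one research lactate, in both arms. Staged Reduction Day 1 (first 24 hours) lists "DPR Group research labs every 6 hrs", lactate among them, alongside 6-hourly infusions. SoC infants have lactate every 24 hours. No line asks for a second lactate before the first infusion.
- **Individual Subject Discontinuation.** "Lactic acid > 5 mmol/L" is one of the criteria at which DPR stops at once. No repeat is asked for, whereas the glucose criterion in the same list must persist for more than 12 hours.
- **Study Discontinuation.** The trial-level rule reads: "The study will be stopped if more than 3 subjects in the DPR group develop any one of the individual subject discontinuation criterion above".
- **Appendix A, Risks and Benefits, Safety Monitoring.** The dialysate contains 40 mmol/L lactate. Lactic acidosis is listed as a possible reaction, and stopping the infusion is part of its management.

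**The concern.** The entry rule for lactate asks for persistence; the stop rule does not. The schedule does not secure the second value that the entry rule needs before treatment starts. A newborn with one high lactate can therefore meet the letter of the eligibility criteria and receive a lactate-containing fluid, at a level where the plan would withdraw that fluid from an infant already on it.

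Two things are at stake. The first is the infant's safety at the first one or two infusions. The second is the safety objective, in which lactate is a named measure. An infant who enters above 5 mmol/L and stays there may have to stop DPR soon after starting, and may use up one of the three events that the study stop tolerates, for a rise that was present beforehand.

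**Working it through.** The plan gives no figure of its own to reproduce here. The check compares the entry and stop limits, followed by short arithmetic.

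**1. Entry limits against stop limits** (Eligibility Criteria; Individual Subject Discontinuation; neonatal AKI table under Safety Monitoring)

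| Measure | Excluded at entry | Stopped on treatment | Can pass this entry limit while past the stop limit? |
|---|---|---|---|
| Lactate, mmol/L | >5 twice, at least 6 h apart | >5 | Yes, e.g. a single 6 |
| pH | ≤7.0 | <7.1 | Yes, e.g. 7.05 |
| Creatinine, mg/dL | >2.0 with anuria | Stage 3 AKI, which ≥2.5 alone satisfies | Yes, e.g. 2.6 without anuria |
| Sodium, mEq/L | <130 or >150 | <125 or >150 | No |
| Potassium, mEq/L | <3.0 or >6.5 | <2.5 | No |
| Glucose, mg/dL | >150 | >250 for more than 12 h | No |

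Three measures have the gap and three do not. The laboratory tests listed at Screening include creatinine but no blood gas, so the pH row matters only when a gas is drawn.

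**2. Can the lactate exclusion operate before dosing?** It needs two values at least 6 hours apart. Screening supplies one. The next scheduled DPR-arm lactates belong to the same 6-hourly day as the infusions, and nothing places one of them before the first infusion.

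**3. Lactate instilled** (dose steps from Set-up for DPR; 40 mmol/L = 0.04 mmol/mL from Appendix A)

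- First bolus: 10 mL/kg × 0.04 = 0.4 mmol/kg.
- Second bolus, if given before the 6-hour lactate result is back: 20 mL/kg × 0.04 = 0.8 mmol/kg.
- Sum: 0.4 + 0.8 = 1.2 mmol/kg.
- The 100 mL cap does not bind at 20 mL/kg unless weight exceeds 100/20 = 5.0 kg.

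These are instilled amounts. Excess fluid is removed after a 1-hour dwell, so the absorbed amount is unknown.

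**4. Study stop.** More than 3 means the fourth infant triggers it. The documents give no rate of lactate above 5 mmol/L, so the rates below are assumptions. With 20 DPR infants, independence, and a chance p that each counts on the lactate criterion, P(4 or more) = 1 − Σ(k = 0 to 3) C(20,k) pᵏ(1−p)²⁰⁻ᵏ:

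| Assumed p | P(4 or more of 20) |
|---|---|
| 5% | 1.6% |
| 10% | 13.3% |
| 15% | 35.2% |
| 20% | 58.9% |

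The table shows only that the rule is sensitive to a few extra counted infants. It does not estimate how many would come from raised entry values.

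**5. Does a held first infusion fit the schedule?** Latest screening at 12 h + 6 h = 18 h, inside the 24-hour window of Staged Reduction Day 1. Blood: 1 mL routine + 2 mL research = 3 mL/day, the plan's stated total, within which the repeat must fit.

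**The case against.** The strongest reply is that the asymmetry may be deliberate: tolerate a transient rise after birth, but be cautious once a lactate-containing fluid is running. A site could also read the verification step as unfinished until a second lactate is in hand. The investigator may exclude any infant thought to be at increased risk, the bicarbonate and other acidosis items will catch some of these infants, and 6-hourly lactates would show a persistent rise quickly.

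Much of this stands. It is why the point concerns what the criteria permit and not what sites will do: the plan does not direct anyone to dose an infant with a high lactate. But it does not require the second value either, and neither verification nor discretion is tied to lactate. A repeat before dosing would keep the tolerance of a transient rise.

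A reader might infer three stronger things that the documents do not support.

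- *That lactate is the only limit out of line.* It is not; pH and creatinine have the same gap.
- *That an infant still above 5 mmol/L must stop and must count towards the study stop.* Both rules use the verb *develop*, and a value already raised before dosing arguably has not developed on treatment. The text does not settle this.
- *That a later high value could not be interpreted.* A baseline lactate is scheduled in both arms and SoC infants have daily values, so change from baseline can be examined. What remains uncertain is why a rise persists in an infant who began above the limit.

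**Conclusion.** The mismatch is in the text and holds. For lactate, pH and creatinine, an infant can satisfy the entry limit while beyond the corresponding stop limit. For lactate, the schedule does not ensure that the exclusion can operate before the first infusion. The exposure is 0.4 mmol/kg instilled at the first bolus, or 1.2 mmol/kg if a second is given before the next result.

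This rests on the infant meeting no other exclusion and on the investigator not using discretion. The documents give no frequency and no harm threshold for the instilled amount, so the number of infants affected is unknown and may be small. The point is a tightening of a design choice, not a text error, and is worth considering because the change is cheap.

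**What to change.** In Eligibility Criteria and its note on laboratory results:

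1. Give the first infusion only if the most recent lactate is at or below 5 mmol/L.
2. If the screening lactate is above 5 mmol/L, hold the infusion and repeat lactate about 6 hours later, and not before 6 hours, so that the existing persistence test is kept. A repeat at or below 5 makes the infant eligible. A repeat above 5 meets the existing two-occasion exclusion, and the infant may be replaced.
3. Apply the same screening check and repeat to SoC infants. Otherwise exclusions after randomization would depend on arm, because SoC lactates are only 24-hourly.
4. Set the pH exclusion at below 7.1, and exclude creatinine of 2.5 mg/dL or more regardless of urine output.

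With items 1 and 2 in place, no infant starts DPR with a latest lactate above the stop limit, so the reading of *develop* matters much less for lactate.

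**Cost.** Infants with a raised first value wait about 6 hours for the first infusion. In the DPR arm the repeat can be timed with the glucose already drawn within 1 hour before infusion; in the SoC arm it is one added draw. There may be a few more exclusions after randomization, which matters somewhat in a trial of 40, though replacement is already allowed.
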